## 10.6 Prior and Concomitant Therapy

The concomitant medication and therapies listed in Section 9.4 should be avoided during the study.

Medication, which is considered necessary for the participants safety and well-being, may be given at the discretion of the Investigator. However, concomitant medication administered during the study may lead to withdrawal of the participant from the study (see Section 9.6).

#### 10.7 Treatment Compliance

Compliance will be noted in the participant diaries. Use of creams will be recorded daily by the participants.

The test and reference creams will also be weighed before dispensing of the creams to the participants, during the study at day 5 and 15, and after return of the creams. Cream consumption (test or reference creams) based on weight will be calculated in order to analyse exposure to treatment. Patients that apply treatment on less than 75% of the days in the study period are considered to be violating the protocol and will be excluded from the per protocol population.

Confidential Page 37 of 65

Version: Version 3.0 Date: 15 August 2019 Sponsor: ACO Hud Nordic AB Study Code: Novum ACO-CT-2018-01 EudraCT No.: 2018-002945-12

## 10.8 Drug Accountability

All study medications supplied for this study should be stored in a secure place. The Investigator or designated person at the study site will keep a record of the inventory and dispensing of all study medications. The Investigator is responsible for the product accountability.

Confidential Page 38 of 65

Version: Version 3.0 Date: 15 August 2019 Sponsor: ACO Hud Nordic AB Study Code: Novum ACO-CT-2018-01 EudraCT No.: 2018-002945-12

## 11 STUDY ASSESSMENTS

## 11.1 Primary and Secondary Endpoints

	Objectives	Outcome measures
Primary	To determine whether applying a new moisturizing cream (the test cream) for 4 weeks is superior in terms of skin barrier strengthening, when compared with (1) no treatment and (2) two reference creams in adults with a predisposition to a skin	
 
Trans Epidermal Water Loss (TEWL) after induction of skin irritation (TEWL on day 31 – TEWL on day 29)
 
Redness after induction of skin irritation (redness on day 31 – TEWL on day 29)
 

	barrier defect.	
Secondary	To determine whether there is a difference between the new moisturising cream (the test cream) and (1) no treatment and (2) the two reference creams in:	TEWL after 4 weeks treatment (day 29-baseline)
		2. Skin moisturisation:
		
 
Capacitance measurements (day 29- baseline)
 

	Resting skin barrier function	
 
Skin surface dryness (3D skin images, day 29-baseline)
 

	
 
Skin moisturisation
 
Tolerability
 
Cream consumption
 
Safety
 
	c. NMF levels on day 29
		3. Tolerability properties:
		
 
Participant tolerability scores by VAS on day 1, day 5 and day 29
 

		
 
b. Investigator visual scores for redness (day 15 – baseline and day 29 – baseline)
 

		
 
c. Objective erythema from 2D colour skin images (day 15 – baseline and day 29 – baseline)
 

		Cream consumption after 28 days of treatment (g)
		5. Number of adverse events
Tertiary	To investigate the number of participants with FLG loss-of-function mutations and investigate and relationshhip with treatment effects	Number of FLG loss-of-function mutation carriers
		

Descriptive tabulations of TEWL by mutation status, if sufficient participants with mutation are detected

Confidential Page 39 of 65

Version: Version 3.0 Date: 15 August 2019 Sponsor: ACO Hud Nordic AB Study Code: Novum ACO-CT-2018-01 EudraCT No.: 2018-002945-12

## 11.2 Efficacy Variables and Assessments

Unless otherwise indicated all procedures will be conducted by the investigative team, comprising experienced skin/dermatology researchers delegated duties by the PI, at the Sheffield Dermatology Research CRF. All assessments will be conducted at each of the 4 treatment sites in each participant unless otherwise indicated. None of the procedures listed would be routinely performed as part of standard clinical care.

## 11.2.1 Skin irritation testing

This test is a previously published method for determining skin sensitivity. It is based upon the skin's response to the standard irritant sodium lauryl sulphate (SLS). Exposure to 1% SLS for 24 hr under occlusion is followed by evaluation of redness and TEWL readings of the transient irritation. The procedure is summarised below:

- 1. Demarcate the test sites; upper volar forearms both sides, 2 patches each (refer to "Test Sites").
- 2. Score visible redness for the test sites using the scales provided
- 3. Capture skin site images as described above (for determination of erythema index)
- 4. Measure objective skin redness (mexameter) and TEWL (as described above) at each patch site
- 5. Apply Finn Chambers (12mm aluminium chambers on Scanpor tape) containing a filter insert and 50µL 1% SLS to designated test sites. Record the time of patch application.
- 6. Cover all test sites with a waterproof adhesive membrane (Patch Protect).
- 7. Instruct the participants to:
  - a. Wash as normal the dressings are water proof
  - b. Contact us if the patches come away before the 24hr period is complete
  - c. Remove the patches themselves in 24hrs (day 30)
  - d. Wash the skin of their forearms with water after removing the patches, and then avoid washing the sites until after the next visit
  - e. Not to apply any products to the patch test sites
- 8.  $24 \pm 2$  hours after patch removal ( $48 \pm 2$  hours after patch application), remark the test sites where necessary
- 9. Locate/demarcate the test sites
- 10. Repeat the visual scoring, image capture and objective assessments of redness, and TEWL.

The procedure is conducted over 49 hours, and involves 60 minutes to conduct the baseline assessments, 40 minutes to apply the patches, 10 minutes to remove them 24 hours later and a further 60 minutes to evaluate the results.

Quantification of skin irritation will support the two primary efficacy outcomes (further details on these variables are provided below):

- 1. Trans Epidermal Water Loss (TEWL) after induction of skin irritation (TEWL on day 31 TEWL on day 29)
- 2. Redness after induction of skin irritation (redness on day 31 TEWL on day 29). Redness is measured using the following techniques (described in more detail below):

Confidential Page 40 of 65

Version: Version 3.0 Date: 15 August 2019 Sponsor: ACO Hud Nordic AB Study Code: Novum ACO-CT-2018-01 EudraCT No.: 2018-002945-12

- a. Visual scoring by the investigator
- b. Measurement of skin redness objectively using the Mexameter
- c. Determination of the erythema index from 2D skin images

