#### **OVERALL STUDY DESIGN:**

Consenting volunteers with atopic dermatitis will be screened against the inclusion/exclusion criteria. Figure 1 and Table 1 illustrate the overall study design and the study flow-chart. Enrolled participants will be randomised to treat the lower or upper parts of the lower volar forearms (i.e. 4 treatment areas) with the new active emulsion (Miniderm Novum), the reference cream Miniderm 20% cream or the reference cream Diprobase cream. One area is left untreated as control. One Finger Tip Unit (FTU) of the creams will be applied twice daily for 28 ( $\pm$  3) days. On day 1 and 29 ( $\pm$  3) the transepidermal water loss (TEWL) and skin capacitance is measured on their forearms to evaluate the effect on skin barrier function and skin hydration. Furthermore, on day 31 ( $\pm$  3), after challenge with 1 % sodium lauryl sulphate (SLS) on day 29 ( $\pm$  3), the susceptibility to irritation caused by SLS will be evaluated visually and by measuring TEWL on their forearms. Study participants will attend visits at the start of randomised therapy and on day 5 ( $\pm$  2), 15 ( $\pm$  3), 29 ( $\pm$  3) and 31 ( $\pm$  3). During the study period the participants will also grade and evaluate the tolerability of the different creams.

INVESTIGATIONAL PRODUCTS (dose, route,	Test product	Miniderm Novum cream (investigational product), 1     FTU twice daily to the previously randomised volar forearm for 28 (± 3) days
administration)	Comparator	Miniderm 20% cream (reference product), 1 FTU twice daily to the the previously randomised volar forearm for 28 (± 3) days
		Diprobase cream (reference product), 1 FTU twice daily to the the previously randomised volar forearm for 28 (± 3) days

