#### 7.1 Study Design and Plan-Description

A prospective phase 2 within-subject multilateral randomised controlled trial to determine the superiority of the test treatment at strengthening the skin barrier compared to no treatment and two reference treatments in adults with a predisposition to a skin barrier defect.

Participants will treat their lower volar forearms for 28 days with three different creams (Miniderm Novum (test cream), Miniderm 20% cream or Diprobase cream) and leave one area untreated as a control. Each forearm will have two different treatment areas and treatment allocation will be randomized (right arm upper, right arm lower, left arm upper, left arm lower). One Finger Tip Unit (FTU) of each cream will be applied twice daily on the designated study area. As such there will be four treatment conditions (with each participant undertaking all 4 treatment conditions):

- 1. No treatment (control),
- 2. Miniderm Novum (test cream),
- 3. Miniderm 20% cream or
- 4. Diprobase cream

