### 10 TREATMENT OF PARTICIPANTS

#### 10.1 Investigational Products

#### 10.1.1 Treatment Regimens

The participants will apply 3 different creams on their lower volar forearms and the treatment area will be randomized. One randomized area will be left untreated. One FTU of the creams will be applied twice daily for 28 (± 3 days).

Sponsor: ACO Hud Nordic AB

EudraCT No.: 2018-002945-12

Study Code: Novum ACO-CT-2018-01

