#### 1. Introduction:

This study is designed in order to evaluate the skin barrier strengthening effects of Miniderm Novum and the two reference creams compared to untreated. It is a randomised, controlled, blinded, four parallel group study.

The participants will apply cream (1 FTU) twice daily on designated treatment areas on their volar forearms for 28 days. On day 5 and 15 the participants will visit the clinic where the test and reference products will be weighed and the diary reviewed. Skin imaging to analyse erythema will be performed on day 1, 15, 29 and 31. On the morning of day 29 the participants will wash their arms and not apply any product. They will visit the clinic and TEWL and skin capacitance will be measured. Small metal cups (Finn chambers) with SLS will be attached to the skin on the 4 treatment areas and the participants will be instructed to avoid showering or heavy exercise to avoid the patches getting wet. On day 30 the participants will remove the patch and leave the skin to recover for 24 hours. On day 31 the participants will visit the clinic and TEWL and skin capacitance will be measured again.

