# 2. Study Methods

# 2.1 Study Design

It is planned to recruit 40 adults (male and female, aged 18 and above) with personal history of atopic dermatitis but no current eczema on the volar forearms and no possible allergy to the ingredients in the study medications.

Four treatment sites on the lower volar forearms (two on the right and two on the left) will be randomised for each participant with one treatment to be applied to each of three sites and the fourth remaining untreated as a control. The four treatment groups are;

- No treatment (control)
- Miniderm Novum (test cream)
- Miniderm 20% (reference cream)
- Diprobase (reference cream)

One Finger Tip Unit (FTU) of each cream will be applied twice daily on the designated study area. The participants will record details of cream application frequency, as well as participant tolerability in a diary.

Subjects will remain in the study for 4-5 weeks.

At each study visit, concomitant medication and any AEs are noted in the Case Report Form (CRF). The study medication will be collected and weighed in order to estimate cream consumption.

Participants will attend 5 clinic visits during the study:

- Visit 1 (screening) will be performed at baseline (Day 1)
- Visit 2 will be performed after 5 days of treatment
- Visit 3 will be performed after 15 days of treatment

- Visit 4 will be performed after 29 days of treatment
- Visit 5 will be performed 1 day after SLS-patch removal (Day 31)

Assessors will be blind to the treatment assigned to each site. Subjects will be blinded to the cream assigned to each study site – although the untreated site will remain unblinded.

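### Internal inconsistency in the primary-endpoint procedure: the SLS patch location in Protocol 11.2.1, step 1, does not match the four treatment areas

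*Protocol*

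**What the plan says.** **Where the creams go.** The Protocol synopsis (overall study design) has participants "randomised to treat the lower or upper parts of the lower volar forearms (i.e. 4 treatment areas"). Protocol 7.1 says "Participants will treat their lower volar forearms for 28 days with three different creams" and names the areas as "right arm upper, right arm lower, left arm upper, left arm lower". Protocol 10.1.1 repeats the region: "The participants will apply 3 different creams on their lower volar forearms and the treatment area will be randomized". SAP 2.1 agrees: "Four treatment sites on the lower volar forearms (two on the right and two on the left"). SAP 6.4 places the TEWL test sites on the same upper and lower parts of each lower volar forearm.

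**Where the SLS challenge goes.** Protocol 11.2.1 gives the numbered procedure behind both primary outcomes. Step 1 reads "Demarcate the test sites; upper volar forearms both sides, 2 patches each" and sends the reader to a description called Test Sites. Step 5 gives no anatomy; it only has the chambers applied "to designated test sites. Record the time of patch application". The SAP Introduction says that the chambers "with SLS will be attached to the skin on the 4 treatment areas".

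**The concern.** Both primary outcomes are changes from Day 29 to Day 31 at SLS-challenged skin, compared between the test cream, no treatment and the two reference creams within each participant. Protocol 11.5 defines a protective effect as lower TEWL after irritation on cream-treated skin than on untreated skin. A patch therefore informs a contrast only if it sits on the area to which that treatment was allocated.

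Step 1 of 11.2.1 is the only place in the Protocol where the numbered procedure gives the patches an anatomical location, and that location differs from the treatment map. Position on the arm is not a trivial detail. SAP 7.9 records that investigators noticed patches may adhere differently along the forearm, and that the skin's reaction may vary with distance from wrist or elbow.

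**Working it through.** The plan gives no figure to reproduce here. The check sets the passages side by side.

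**1. Locations given**

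| Source | What is located | Location |
|---|---|---|
| Protocol synopsis | Treatment areas | Upper or lower part of each lower volar forearm |
| Protocol 7.1 | Treatment areas | Lower volar forearms; one upper and one lower area per arm |
| Protocol 10.1.1 | Creams | Lower volar forearms |
| SAP 2.1 | Treatment sites | Lower volar forearms, two per arm |
| SAP 6.4 (TEWL) | Test sites, Days 1, 29 and 31 | Upper and lower part of each lower volar forearm |
| Protocol 11.2.1, step 1 | Test sites for SLS | Upper volar forearms, two patches per arm |
| SAP 1 | SLS chambers | The four treatment areas |

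**2. Patch count.** 2 patches × 2 forearms = 4 patches, against 4 treatment areas. The number agrees; only the location conflicts.

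**3. Literal readings of step 1**

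- *Reading A: the upper volar forearm is a different region from the lower volar forearm.* All four patches lie outside the treatment areas, so 0 of 4 areas are challenged.
- *Reading B: upper means the upper part of the lower volar forearm.* Each arm has one upper area, and step 1 puts two patches on each arm. Both fall in that arm's upper area, so 2 of 4 areas are challenged and 4 − 2 = 2 are not. Each participant then has two challenged treatments and so a single within-participant contrast. That is at most one of the three planned contrasts, and none of them if the test cream was allocated to a lower area.

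The design needs 4 of 4, one patch per area. Neither reading gives it.

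**4. Does other text settle the location?**

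- Protocol 10.2 uses the term test sites for the places to which treatments are allocated. On that usage, marking the test sites means marking treatment areas.
- Protocol 11.2 sends all assessments to each of the four treatment sites, but allows exceptions where a procedure says otherwise. Step 1 does name a location, so this rule does not clearly override it.
- Protocol 11.5 compares treated with untreated skin after irritation, which requires patches on both.
- SAP 6.4 takes TEWL on Days 1, 29 and 31 at the same test sites, all on the lower volar forearm.
- SAP 1 states the location outright, but in the introduction to an analysis document rather than in the procedure.
- The Test Sites cross-reference in step 1 matches no section title in the Protocol's table of contents.

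The intent can be recovered from these passages. The wording of step 1 still contradicts it.

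**The case against.** The strongest reply is that the documents already answer the question. The SAP Introduction puts the chambers on the treatment areas. Protocol 10.2 gives test sites the meaning of treatment sites, and that is the term used throughout 11.2.1. The general rule in 11.2 and the rationale in 11.5 agree. The four patches match the four areas, and the study's own labels use upper for part of the lower forearm, so the phrase in step 1 looks like a garbled label. In addition, 11.2.1 calls itself a summary. The cross-reference may be resolved in the design figure or in the case record forms listed in Appendix A, neither of which is available here.

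Most of this stands. It makes a wording slip the likely explanation, and it rules out any statement about what staff actually did. It does not make step 1 correct. The one explicit statement of patch location that agrees with the treatment map is in the SAP, while the numbered procedure is in the Protocol and says something else.

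A reader might infer that the challenge was planned or carried out on untreated skin, so that all three primary contrasts have an expected difference of zero. That follows only under Reading A, applied by staff who disregarded Protocol 10.2, 11.2 and 11.5. A reader might also want to discount the 3.5 g/m²/h target difference by some rate of misplaced patches. The documents give no such rate, and a wrong instruction would misplace patches systematically rather than at random. No such figure is supported.

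**Conclusion.** The inconsistency is real and sits in the procedure for both primary outcomes. Followed literally, step 1 would challenge 0 of 4 or 2 of 4 treatment areas, depending on what upper is taken to mean. The other passages indicate that all four areas were meant, so this is probably a drafting slip. Nothing in the documents shows that a patch was misplaced or that the primary data are affected.

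The conclusion rests on the text alone and assumes that no document outside the two reviewed already fixes the patch positions. If the case record forms or the figure do so, the residual issue is that step 1 disagrees with them. The step should be corrected because it is an operative instruction for the primary endpoint. It is not evidence against the design.

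**What to change.** Reconcile step 1 of Protocol 11.2.1 with the synopsis, 7.1, 10.1.1, 10.2, 11.2 and SAP 1. Replace the location with one SLS patch within each of the four randomised treatment areas (upper and lower area on each lower volar forearm). Either supply the Test Sites description to which the step refers or delete the reference.

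If visits have begun, confirm where patches were actually placed before unblinding. The blind data review in SAP 5 and 7.9 already considers location and patch adherence, so this adds one item to it. The documents do not state recruitment status. However, the study period in Protocol 7.4 (February to April 2019) precedes the date of Protocol version 3.0 (15 August 2019), so the check may well be needed.

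The cost is a minor protocol amendment, which Protocol 14.1.1 requires to go to the ethics committee. Sample size, analysis model and treatment allocation are unchanged.

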## 11.2.2 Trans Epidermal Water Loss

Skin barrier function will be evaluated by measuring the Trans Epidermal Water Loss (TEWL) of the untreated area and the areas treated with creams, before and after treatment (secondary outcome). TEWL will also be measured before and after induction of skin irritation by application of SLS (see "induction of skin irritation") as a means of quantifying skin irritation (primary outcome). TEWL measurements, recorded in g/m²/h, will be performed using an AquaFlux AF200 condensing chamber probe (Biox Systems Ltd., London, UK).

Three repeat TEWL measurements, taking ~2 minutes each, will be collected at each site. Measurements will be repeated if an anomaly occurs during measurement (i.e. deviation from a typical bell shaped TEWL curve), which can occur if a participant becomes uncomfortable, or if the reading appears abnormally low or high. In either event the measurement will not be taken until at least 4 minutes has passed from the collection of the first measurement to permit restoration of normal TEWL. If TEWL was retaken due to a measurement anomaly the first reading will be discarded. If the reading was repeated for any other reason both measurements will be recorded the average of all readings will be used for subsequent analysis. After use in each participant the probe will be decontaminated with a 70% alcohol wipe.

All assessments will be performed in a room maintained at 21  $\pm$  2  $^{\circ}$  C and 38–50% relative humidity according to published guidelines (38). All test sites will be acclimatized to room conditions for 20-30 min before assessment.

## 11.2.3 2D Skin Imaging of erythema

A single close-up (50x magnification) image of each skin site will be captured using the c-cube camera with glass lens (Pixience, France). Each image takes approximately 5 minutes to capture. A 16x12mm area of the test site skin is imaged therefore there are no data confidentiality concerns. Captured 2D images are analysed to determine the skin erythema index (degree of redness, arbitrary numerical value) for the region of interest. This quantitative metric supports the primary outcome and the secondary tolerability outcome. The images are stored by the c-cube clinical database software within a protocol specific folder locally and on the server within the study specific folder.

#### 11.2.4 Visual scoring of skin redness

Visual redness will be scored by an experienced grader using the scale below to assess both tolerability (secondary outcome) and skin irritation following patch/irritation testing (primary outcome). The assessment takes no more than 2 minutes.

**Table 9.3:** Visual assessment scale for erythema

Score	Description
0	No reaction.

Confidential Page 41 of 65

Version: Version 3.0 Date: 15 August 2019 Study Code: Novum ACO-CT-2018-01 EudraCT No.: 2018-002945-12

Sponsor: ACO Hud Nordic AB

0.5 / +	Slight, patchy erythema – barely perceptible	
1	Slight uniform erythema – mild erythema	
2	Moderate, uniform erythema – Moderate erythema	
3	Strong erythema – Marked erythema	

## 11.2.5 Objective skin redness

Skin redness will be measured 3 times within each patch test site using a C&K Mexameter probe to quantify SLS-induced skin irritation (primary outcome measure). All 3 measurements (arbitrary numerical scale) will be recorded. A fourth measurement should be collected if the variation is deemed to be too great (at the discretion of the Investigator), under which circumstance all 4 measurements will be recorded (no measurement is discarded). After use in each participant the probe will be decontaminated with a sanitation/detergent wipe. It takes approximately 5 minutes per test site to perform this procedure (20 minutes in total)

